Sustainable HIV Risk Reduction Strategies for Probationers (DRR2)

NCT #02777086

April 8, 2020

We developed a multi-session, brief tablet app, *StaySafe*, designed to improve decision making around health risk behaviors for people under community supervision who had substance use disorders. As part of a randomized clinical trial testing post-treatment outcomes hypothesized to be associated with *StaySafe* administration, this study examines improvements in decision-making skills associated with reductions in health risk behaviors, especially those involving HIV and Hepatitis B or C (for more detail on *StaySafe* development and the research protocol, refer to Lehman et al., 2018).

1.1 Decision-making and Analytically-created Schemas

StaySafe is based on cognitive processing models derived from Analytically-Created Schemas (ACS) and TCU Mapping Enhanced Counseling (MEC; Dansereau, 2005; Dansereau & Simpson, 2009) that include experiential and analytic systems (Kahneman, 2011; Klacynski, 2005). Experiential systems reference previous experiences (Kahneman, 2011; Weber & Johnson, 2009) believed to be used in making decisions about risk behaviors because they are rapid and refer to familiar behaviors, even those with negative outcomes. Analytic systems are typically slower because they often require conscious referencing and reinforcement. Schemas using the analytic system are created through repetition and practice.

The ACS approach can be a vehicle for organizing information through a series of steps and exercises that develop analytic thinking. Exhibiting options visually when developing plans and making decisions can contribute to an objective evaluation of available choices (Dansereau et al., 2013). This can help individuals monitor and control decision making (metacognition), increase knowledge in specific areas (e.g., substance use, treatment initiation, etc.), and improve judgment and behavioral choices (self-regulation). Analytic repetition (similar to practice in athletic training) can develop procedural memory (i.e., skills and tasks that can be stored in long-term memory) that can be accessed rapidly. This process, developed by repetition, can then be used in real-life contexts rather than the more labor-intensive analytic processing. The goal of the *StaySafe* intervention is to replace or “override” inaccurate or maladaptive

information, expectations, and behavior patterns with accurate health-related information and appropriate attitudes and behavioral choices.

1.2 *WaySafe*

The ACS-based tablet app that is used in this study grew out of an NIH-funded disease risk reduction study of *WaySafe*, a group-based curriculum that used an ACS approach to help people in prison-based substance use treatment make better decisions around health risk behaviors when they return to the community. The highly interactive curriculum relies on MEC to prepare individuals for the transition back to the community by demonstrating interrelationships among constructs including problem recognition, commitment to change, and strategies for avoiding behavioral health risks; key information for developing plans to address risky situations. Research has shown that, when compared to standard practice (SP), participants randomly assigned to *WaySafe* groups had greater improvements on knowledge and confidence measures related to HIV information and testing, avoiding risky sex and substance use, and risk reduction skills (Joe et al., 2019, Lehman et al., 2015, Lehman et al., 2019).

1.3 *WORKIT*

WORKIT, a major component of *StaySafe*, is a specific ACS schema that teaches a simplified structure for analyzing problems, weighing and rating options to make a decision, and then planning how to carry out that decision -- **What** is the problem; **Who** is affected by the problem; **Who** can help with the problem; **Options** for dealing with the problem; **Rating** the options; **Knowing** what to do based on the ratings; **Imagining** steps to carry out the decision; and then **Testing** those steps. Several studies using *WORKIT* have shown improved decision making, self-awareness, and problem recognition (Becan et al., 2015; Knight et al., 2015, 2016).

1.4 *StaySafe*

StaySafe was developed as a self-administered Android app for people participating in treatment while under community supervision, targeting decision-making skills to reduce health risk behaviors. Based on *WaySafe*, *StaySafe* uses the *WORKIT* ACS with accompanying health

information facts to train users in making more systematic and informed decisions (Lehman et al., 2018). The intervention includes 12 weekly sessions for participants to learn the WORKIT ACS through systematic repetition.

1.5 Research goals

A randomized clinical trial was conducted to address three primary research goals around the *StaySafe* app: 1) examination of the participation rates of *StaySafe* sessions, 2) test of the effect of *StaySafe* on knowledge, confidence and motivation around health risk behaviors and better decision-making skills, and 3) assessment of the relationship between greater *StaySafe* participation and greater pre-post change from baseline to follow-up time points.

2. Methods

2.1 StaySafe intervention

StaySafe includes 12 brief (10 minutes) self-administered sessions on a tablet; one session per week. Nine of the sessions involve the WORKIT ACS and three Participant Choice sessions include several information-based activities around HIV and health risks.

The first *StaySafe* session presents the participant with an overview of how to navigate through the *StaySafe* app, followed by a demonstration of a WORKIT exercise. Those sessions featuring WORKIT start with choosing from a list of 11 problem themes related to (1) people (e.g., “Asking a partner about his or her HIV testing”), (2) places (“Favorite high-risk places to hang out”) or (3) things (“Practicing safe sex”). Topics were designed to be relevant for people under community supervision with substance use disorders, incorporating feedback from probation officers, substance use treatment counselors, and recommendations from the Center for Disease Control and Prevention (CDC) and the National Institutes of Health (NIH) on reducing health risks.

After choosing a topic (**What** is the problem?), the participant views a vignette showing actors working through a risky situation (vicarious learning), prior to proceeding through the rest of the WORKIT steps. Some of the WORKIT steps involve selecting from a list of possible

responses to questions such as “Who is affected by the decision?” or “Who can help with the problem?” For the WORKIT step, “Options for dealing with the problem,” participants select from a series of four options that are related to the chosen topic. For example, two of the options for the problem theme, “It’s hard to ask a partner about his or her HIV testing,” are “Don’t ask, but always use condoms,” and “Have unprotected sex just this one time.” Supporting health facts for each option “pop up” on the screen, thus providing educational information embedded within the decision-making schema. Mental practice such as this is deemed to help prepare the participant for using the WORKIT schema in the “real world” and therefore an effective way to learn (Cooper et al., 2001). The goal is not to have the participant solve specific problems during sessions, but through repeated practice using relevant examples across multiple *StaySafe* sessions, to internalize the schema. A final activity in the WORKIT sessions is a “maze” game in which an animated character moves around a maze as participants responded to quiz questions designed to reinforce information from the session.

Participant choice sessions are interspersed among the WORKIT sessions in order to provide more in-depth information about HIV and health risks and to vary the tablet presentations. Three different activities were offered including (1) a CDC video giving information about HIV/AIDS, (2) an information page about HIV/AIDS with a brief discussion about HIV medication therapy or someone affected by HIV/AIDS talking about their experience, and (3) the maze game with additional question content. Participants chose one or more of the activities.

2.2 Procedures

The study took place at five community supervision and corrections department (CSCD) facilities in three large counties in Texas; these included two CSCD community-based locations and three residential facilities. In the community-based facilities, recruiting materials included flyers, posters, and brief presentations at the beginning or end of orientation or group sessions; additionally, the research team spoke with individuals in CSCD waiting rooms about the study

opportunity. All recruiting was conducted by TCU researchers. At the CSCD residential facilities, researchers provided a brief overview of the study to groups of new client admissions within a week of their arrival into the substance use treatment program. Those interested in participating completed TCU IRB-approved informed consent and brief demographic forms. Participants completed baseline surveys the following week according to individual community supervision schedules. Community-based site participants also provided contact information for receiving meeting reminders about study data collection appointments. Participants were randomized into study conditions (i.e., *StaySafe* and SP arms) following completion of the baseline survey packet. The project utilized a permuted block randomization approach, with block size varying randomly between 2, 4 or 6.

2.2.1 Data Collection. Sources of data used for the project included surveys and tablet data. Participants in both conditions completed surveys, and those in the *StaySafe* condition also contributed tablet data. In community facilities, researchers coordinated survey administration and tablet sessions with participants on the same day as their required community supervision activities (e.g., treatment groups and meetings with counselor or probation officer [PO]). A subset of individuals in the *StaySafe* arm who had completed at least six tablet sessions were also invited to interview with a senior member of the research team about the *StaySafe* experience. Qualitative results are reported in Pankow et al. (2019). For those in the community locations, participants were handed a scheduling card with the date/time of the next study activity and a contact number for the researcher in case of scheduling conflicts. In residential facilities, scheduling was coordinated with program staff who provided the researcher with a list of available time slots when participants were free to complete study activities.

2.2.2 StaySafe sessions. The 12-session *StaySafe* intervention was designed to be administered one session per week for 12-weeks post consent. In cases where a participant missed a week, two sessions were administered in a single week. Sessions were completed on a hand-held Android tablet, and participants were provided with headphones to listen as a

narrator relayed the content of each tablet screen. Researchers utilized a tracking system (developed for the study) to coordinate data collection and manage the history of completed activities. Participant survey and tablet session data were linked by a study identification number; no identifiable information was recorded on the data sources.

2.3 Data collection and measures

Paper and pencil surveys were administered at baseline prior to random assignment and again three months after baseline. Outcome measures included the TCU Confidence & Motivation scales, and three decision-making scales – Rational decision-making, Dependent decision-making, and the TCU Decision-making scale. The surveys also included demographic and background measures from the TCU A-RSK form (IBR, 2008). Variables included age, gender, race/ethnicity, education, marital status, and in the last six months before entering their current program – employment, public assistance, arrested, on parole or probation, in jail or prison, and treatment in an emergency room, for mental health, alcohol use, and illegal substance use.

2.3.1 TCU Knowledge, Confidence, and Motivation scales (KCM). Four scales included *HIV Knowledge Confidence, Avoiding Risky Sex, HIV Services & Testing, and Risk Reduction Skills*. Each of the scales, except for *HIV Services & Testing*, included items that assessed how knowledgeable (K) the participant felt about the topic, how confident (C) they were about their knowledge, and how motivated (M) they were to act on the knowledge. *HIV Services & Testing* only included knowledge and motivation items (Lehman et al., 2015). The knowledge, confidence, and motivation components for each scale were included in an overall score as well as examined as separate subscales.

The TCU *HIV Knowledge Confidence* scale has 13 items (alpha = .93) and sample items include “You know enough to teach others what they should do if they think they have been exposed to HIV” (K), “You feel very confident that you could be a role model for others in helping reduce HIV risks” (C), and “You are totally committed to helping your friends and/or

family avoid HIV/AIDS" (M). Coefficient alpha reliabilities for the three subscales ranged from .75 to .88. The TCU *Avoiding Risky Sex* scale has 13 items (alpha = .93 and ranged from .81 to .84 for the three subscales) and includes items such as "During the past month, you have learned about what situations might lead you to make a poor decision about risky sex" (K), "During the past month, your confidence in managing emotions in sexual situations in the real world has increased" (C), and "During the past month, you have become more motivated to protect your sexual partner from HIV risk in the real world" (M). The TCU *HIV Services & Testing* scale consists of 7 items (alpha = .81 for the full scale, .62 and to .79 for the knowledge and motivation subscales respectively). Sample items include "During the past month, you have become more knowledgeable about how to get HIV services in the real world" (K) and "You will get tested for HIV if you think that you might have been exposed" (M). The TCU *Risk Reduction Skills* scale is comprised of 14 items (alpha = .91 and ranged from .65 to .82 for the three subscales) and includes items such as "During the past month, you have a better understanding of how your shoulds and wants can conflict in the real world" (K), "During the past month, you have become more confident in balancing your shoulds and wants in the real world" (C), and "During the past month, your motivation to avoid personal HIV risks in the real world has increased" (M).

All items for the TCU Confidence & Motivation scales use a 5-point Likert-type response scale ranging from 1=Disagree Strongly to 5=Agree Strongly. Items worded in the opposite direction from the scale construct were reflected by subtracting the score from 6. Scale scores were then computed by calculating the average score for items within the scale then multiplying the average score by 10 to obtain a range from 10 to 50. Scores above 30 indicated at least some agreement with the scale construct and scores below 30 indicated at least some disagreement.

2.4 Analytical approach

Three primary sets of analyses were conducted. In the first set, characteristics of the research sample are reported and *StaySafe* participation in terms of number of sessions completed by the *StaySafe* group are calculated. A second set of analyses compared the *StaySafe* and SP groups on baseline and post-intervention measures using SAS Proc GLM. Analyses were conducted separately for the community and residential samples. The *StaySafe* and SP groups were first compared on demographic and background variables, and baseline measures of the outcome variables to check for group equivalence. The *StaySafe* and SP groups were then compared on outcome variables from the post-intervention surveys using the appropriate baseline measure as a covariate. Effect sizes (Cohen's d) were computed for each outcome measure by taking the difference between least square means of the *StaySafe* and SP groups and dividing by the standard deviation of the SP group (Cohen, 1988).

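### Each setting's StaySafe versus SP comparison pools two or three facilities without a facility term, which costs some precision but causes no bias

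*Combined protocol and SAP*

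**What the plan says.** Section 2.2 (Procedures): "The study took place at five community supervision and corrections department (CSCD) facilities in three large counties in Texas". Two of the five are community sites and three are residential. Allocation followed the baseline survey, and its method is given as: "The project utilized a permuted block randomization approach, with block size varying randomly between 2, 4 or 6". No stratification by facility, county or setting is stated.

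Section 2.4 (Analytical approach): "Analyses were conducted separately for the community and residential samples". Within each sample the arms are compared in SAS Proc GLM, "compared on outcome variables from the post-intervention surveys using the appropriate baseline measure as a covariate". No facility or county term is named. Facility is also absent from the background variables listed in section 2.3, which feed the check of group equivalence. Cohen's d is the difference in least-squares means divided by the SD of the SP group.

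SP is spelled out only in section 1.2, as standard practice in the earlier WaySafe research. Its content in this trial is not described.

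**The concern.** Recruitment, surveys and tablet sessions were all organised around a facility, so each participant's facility is known. Residential participants were approached "within a week of their arrival into the substance use treatment program". Community participants were seen on days when they attended supervision or treatment. What a facility teaches over the three months to follow-up could move the same outcomes that StaySafe targets.

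The baseline score removes facility differences present at entry. It does not remove differences that arise afterwards. This matters for these scales because many of the sample items in section 2.3.1 ask what has changed in the past month, and the past month at follow-up is a different period from the past month at baseline.

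The consequence depends on how the blocks were run:

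- **Blocks run within facility:** the arms are nearly balanced on facility, but the pooled model leaves between-facility variance in its error term. Its standard error is too large and its test too cautious.
- **Blocks not run within facility:** the arms can differ by chance in facility mix. This adds noise to the contrast, and the pooled standard error already reflects it.

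In both cases a known factor that could sharpen the comparison goes unused.

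**Working it through.** **Inputs from the documents.** Two community and three residential facilities; individual randomisation in permuted blocks of 2, 4 or 6; baseline score as the only covariate named; settings analysed separately. The documents give no sample size, significance level, power or between-facility variance, so there is no figure of the plan's own to reproduce.

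**Assumptions.** Two-sided 5% test. Let ρ be the share of baseline-adjusted outcome variance that lies between facilities within a setting; 2%, 5% and 10% are shown.

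**Formulas.**

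- Ratio of standard errors, without versus with the term: 1/√(1−ρ).
- Sample size needed without the term, relative to with it: 1/(1−ρ).
- Power with the term, for an effect that has 80% power without it: Φ((1.960 + 0.842)/√(1−ρ) − 1.960).
- Actual level of the pooled test if blocks were run within facility: 2(1 − Φ(1.960/√(1−ρ))).

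| ρ | SE ratio | Sample size ratio | Power with term | Actual level, blocks within facility |
|---|---|---|---|---|
| 0.02 | 1.010 | 1.020 | 80.8% | 4.8% |
| 0.05 | 1.026 | 1.053 | 82.0% | 4.4% |
| 0.10 | 1.054 | 1.111 | 84.0% | 3.9% |

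Worked line for ρ = 0.10: 1/√0.90 = 1.054. Power is Φ(2.802 × 1.054 − 1.960) = Φ(0.993) = 84.0%. The level is 2(1 − Φ(1.960 × 1.054)) = 2(1 − Φ(2.066)) = 3.9%.

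The power column treats the pooled standard error as the true SD of the estimate, which fits blocks not run within facility.

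**Chance imbalance when blocks are not run within facility.** For two equal-sized facilities whose means differ by D residual SDs, with n per arm, the chance contribution to the arm contrast has SD D√(2 × 0.25/n). With D = 0.5 and n = 50 (assumed), this is 0.5 × √0.01 = 0.05, a 95% range of about ±0.10 residual SD. With D = 0.2 to 0.8 at the same n, the range is about ±0.04 to ±0.16.

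**Simulation check.** 4,000 trials per scenario, three facilities, blocks of 2, 4 or 6, baseline-adjusted model with and without facility.

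- Facility effects of −0.4, 0 and +0.4 on a residual variance of 0.75 give ρ = 0.107/(0.107 + 0.75), about 0.125.
  - The pooled estimate averaged 0.40 for a true effect of 0.40 under both block schemes.
  - Under no effect, the pooled test rejected in 5.5% and 5.0% of trials (total N of 100 and 200) when blocks ignored facility, and in 3.8% and 3.6% when they were run within facility. The Monte Carlo standard error at 5% is √(0.05 × 0.95/4000), about 0.3 percentage points.
  - Power without versus with the term at N = 100 was 56% versus 61% (blocks ignoring facility) and 57% versus 62% (within facility). At N = 200 it was 86% versus 90% and 87% versus 90%.
- Facility effects of −0.2, 0 and +0.2 (ρ about 0.034) gave a gain in power of about 1 percentage point.

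The simulation covers three facilities only. The formulas do not depend on the number of facilities, apart from the degrees of freedom used.

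**The case against.** The strongest reply is that nothing here threatens validity. Individuals were randomised, so facility is not confounded with arm by design. A reader might infer from the missing term that the estimated effect is biased by facility, or that false positives are more likely. Neither follows: the pooled estimate is unbiased over randomisations, and the test holds its level or is mildly conservative. Chance imbalance in facility mix is ordinary sampling variation. This part of the reply stands in full.

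A reader might also take it as given that SP is whatever each facility provides, that StaySafe was delivered on top of it, and that care differs between facilities of the same type. The documents state none of these. They mention treatment groups, meetings with counsellors or probation officers, and a residential programme, without describing content by site. Differing care is a reasonable inference, no more. The most visible contrast, community versus residential, is already removed by analysing the settings separately.

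The size is also unknown, and at a share of 5% or less the gain is small. The introduction refers readers to a separate publication for more detail on the research protocol, so the randomisation strata may be given there.

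Finally, section 2.4 is in the past tense, so a new covariate may be a post hoc change. That bears on how the adjusted result is labelled, and does not argue against producing it. What the reply leaves untouched is that a known factor with two or three levels is omitted at a cost in precision that is easy to avoid.

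**Conclusion.** The omission is real and its consequence is modest. It is a loss of precision, with neither systematic bias nor type I inflation. Over assumed facility shares of 2% to 10%, confidence intervals are about 1% to 5% wider than they need be, and an effect with 80% power in the pooled model would gain about 1 to 4 percentage points. If blocks were run within facility, the nominal 5% test runs slightly below its level.

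These sizes rest entirely on the assumed shares and the 5% level. If facilities of the same type differ little, almost nothing is lost. The change is still worth making because it uses information already held and costs very little.

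**What to change.** In section 2.4, add facility as a fixed class factor beside the baseline score in each setting's StaySafe versus SP GLM. Two or three levels are too few to estimate a random effect. Take the least-squares mean difference and its confidence interval from that model. This difference is the numerator of Cohen's d; keep the SP-group SD as the denominator, as the plan defines it.

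In section 2.2, state whether the blocks were run within facility, so that readers can tell which of the two situations applies.

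If the pooled analyses have already been run, leave them as reported and give the facility-adjusted model as a labelled additional analysis.

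The cost is one class variable, a sentence or two of text, and 1 degree of freedom in the community sample or 2 in the residential sample. No new data are needed. The downside is that the gain is slight if facility differences are small.

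### Does dividing by the SP group's standard deviation alone make the reported Cohen's d unsound?

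*Combined protocol and SAP*

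**What the plan says.** Section 2.4 compares StaySafe with standard practice (SP) on "baseline and post-intervention measures using SAS Proc GLM". The post-intervention comparison is made "using the appropriate baseline measure as a covariate", so it is an ANCOVA. On the effect size it says: "Effect sizes (Cohen's d) were computed for each outcome measure", with the numerator obtained "by taking the difference between least square means" of the two arms and the denominator by "dividing by the standard deviation of the SP group (Cohen, 1988"). On the two types of site: "Analyses were conducted separately for the community and residential samples".

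The plan does not say whether the SP SD comes from baseline or follow-up. That the SD is taken within each setting is implied by the separate analyses but not stated. No comparison or pooling of effect sizes across settings is planned.

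**The concern.** Cohen's d is commonly understood as a mean difference over the SD pooled across arms. A reader who sees that name in a results table may set the value beside pooled-SD values from other trials. The plan's denominator uses one arm only, so the two agree only if the arms have similar spread.

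Three further points seem to add weight. The ANCOVA assumes one common within-arm variance, which might suggest that a pooled SD is the natural partner. Using one arm means estimating the SD from about half the participants. And with each setting analysed on its own, the same difference in scale points could appear as two different effect sizes. Since this is the only effect-size measure that the plan defines, a real fault would touch every outcome.

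**Working it through.** The documents give no sample size, SD or effect-size value, so there is no figure of the plan's to reproduce. Inputs from the documents are the formula, model and separate analyses (Section 2.4), the 10 to 50 range of the TCU Confidence & Motivation scales (Section 2.3), and a "permuted block randomization approach, with block size varying randomly between 2, 4 or 6" (Section 2.2). The allocation ratio is not stated.

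Assumed: 1:1 allocation; n = 25 to 150 per arm per setting; baseline-outcome correlation ρ = 0 to 0.7; true effect d = 0.2 to 0.8; SD ratio k = SD(StaySafe)/SD(SP) = 0.7 to 1.3.

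**1. Size of the difference in definition.** With equal arms, (SP-SD effect)/(pooled-SD effect) = √((1 + k²)/2).

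| k | Ratio |
|---|---|
| 0.7 | √(1.49/2) = 0.863 |
| 0.8 | √(1.64/2) = 0.906 |
| 1.0 | 1.000 |
| 1.2 | √(2.44/2) = 1.105 |
| 1.3 | √(2.69/2) = 1.160 |

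The gap runs from -14% to +16%, and is zero when the SDs are equal.

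**2. Precision of the SD.** Its relative standard error is 1/√(2·df). At 50 per arm, SP only has df = 49, giving 1/√98 = 10.1%. Pooled has df = 98, giving 1/√196 = 7.1%. This is the precision of the denominator, not of the effect size.

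**3. Precision of the effect size, equal variances.** In large samples, Var = 2(1 - ρ²)/n + d²/(2·df), with df = n - 1 for the SP SD and 2n - 2 for the pooled SD. For n = 50, ρ = 0.5, d = 0.5:

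- Pooled: 2(0.75)/50 + 0.25/196 = 0.0300 + 0.0013; standard error 0.1768.
- SP only: 0.0300 + 0.25/98 = 0.0300 + 0.0026; standard error 0.1804.
- Ratio 1.020.

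The uncertainty in the mean difference dominates. Over the whole grid, the SP-SD standard error is larger by 0.3% to 0.5% at d = 0.2, by 1.5% to 3.0% at d = 0.5, and by 3.7% to 6.8% at d = 0.8. An ANCOVA simulation (20,000 replicates per scenario; n = 25, 50, 100; ρ = 0.5, 0.7) gave 0.8% to 2.7% at d = 0.2 and 2.6% to 5.3% at d = 0.5.

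**4. Fit with the ANCOVA.** Under equal variances the SP SD and the pooled SD estimate the same quantity, and the test of the adjusted difference uses neither. Nor does a pooled raw SD match the model's own residual SD: dividing by the residual SD would enlarge the effect by 1/√(1 - ρ²), which is 1.15 at ρ = 0.5 and 1.40 at ρ = 0.7.

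**5. The two settings.** Take a 2-point difference in each setting, with an SD of 5 in both arms of one and 8 in both arms of the other. The SP SD gives 2/5 = 0.40 and 2/8 = 0.25. The pooled SDs are √((25 + 25)/2) = 5 and √((64 + 64)/2) = 8, so the pooled version also gives 0.40 and 0.25. The cause is standardising within each setting, not the use of the SP arm.

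**The case for a change.** The best case for a change is that the name and the formula disagree within one sentence, and that the reach is wide. Section 2.3 lists four knowledge, confidence and motivation scales with 3 + 3 + 2 + 3 = 11 subscales, and three decision-making scales. That makes up to 4 + 11 + 3 = 18 outcomes per sample, or 36 values over two samples. Unequal spread is also plausible: scores are obtained by "multiplying the average score by 10 to obtain a range from 10 to 50", and an intervention that moves people towards the upper end could narrow the StaySafe distribution. The time point of the SP SD is not stated, and no interval or difference in scale points is promised alongside.

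The loose label stands. So does the unstated time point, though analysts would ordinarily fill that gap: the sentence follows directly from the post-intervention comparison, which points to the follow-up SD of the SP arm in the sample being analysed. Differences in scale points and intervals would be a useful addition to a report, but their absence does not make the defined statistic wrong.

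The possibility of unequal spread argues as much for the plan's choice as against it. If StaySafe alters the spread, the SP SD keeps that effect out of the denominator. Nor can unequal spread be combined with the precision argument: the -14% to +16% gap needs unequal SDs, while the claim that pooling simply uses more data on the same quantity needs equal ones.

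**Conclusion.** The label is imprecise, but the analysis is sound and no change to the plan is needed. What is called Cohen's d is a control-SD effect size of the Glass type, and the formula is given in full, so a reader can see what was computed. Renaming it would alter no estimate, test or conclusion. Replacing the SP SD with a pooled, baseline or cross-setting SD would swap one defensible standardiser for another, a choice on which statisticians reasonably differ.

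If the arms have equal variance, the cost is a standard error up to about 3% larger by formula and about 5% larger by simulation for effects up to 0.5, and up to about 7% by formula at 0.8. If the SDs differ by 20% to 30%, the value departs from pooled-SD d by about 9% to 16%, and only someone who ignores the stated formula would be misled. Differences between settings would arise with a within-setting pooled SD as well, and the plan does not compare effect sizes across settings. These sizes assume 1:1 allocation and the ranges listed above; the documents do not allow a calculation specific to this trial.
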